**LIST OF ABBREVIATIONS**

AE	Adverse Event
AK	Actinic Keratosis
BT	Bluetooth low energy
CAT	Computer Adaptive Test
CFR	Code of Federal Regulations
CPD	cyclopyrimidine dimer
CRF	Case Report Form
ELISA	Enzyme Linked ImmunoSorbent Assay
IC	Informed Consent
ICF	Informed Consent Form
IRB	Institutional Review Board
IS	Immunosuppressive
LN2	Liquid nitrogen
NCI	National Cancer Institute
NIH	National Institutes of Health
PI	Principal Investigator
NMSC	Non-Melanoma Skin Cancer
PROMIS	Patient Reported Outcome Measurement Information System
SAE	Significant Adverse Event
SCC	Squamous Cell Carcinoma
SPF	Sun Protection Factor
UV	Ultraviolet Light
UVI	Ultraviolet Index
WC	Weill Cornell Medical College

## PROTOCOL SUMMARY

Title:	Validation of shade, a wearable ultraviolet light monitor, for reduction of actinic keratosis
Summary:	
The incidence of non-melanoma skin cancers, due to increased ultraviolet (UV) exposure, has increased by 300% over the past 2 decades. The innovative UV sensor, Shade, is designed to help people manage their UV exposure by quantifying their UV exposure levels through a linked smartphone application. In order to validate the effectiveness of Shade, we propose conducting a study communicating the level of UV exposure and correlating it with the development of actinic keratosis (AK), a precancerous lesion of the skin. We will recruit patients with multiple AKs. We will include renal transplant patients as this population develop AKs as well. We will evaluate the UV monitor's effectiveness in decreasing the number of AKs over a summer. This randomized partially blinded study will recruit 120 patients with a recent history of AKs and evaluate the incidence of new AKs after one summer. We will perform a control versus study group analysis. Half of the subjects (study group) will be randomly assigned to use the sensor along with its smartphone application, while the other half (control group) will receive standard of care treatment involving counseling to avoid sun exposure. Subjects will have regular standard of care visits with the dermatologist who will follow the number of actinic keratosis via clinical exam and photography. The primary outcome will be a statistically significant reduction by at least 25% of the cumulative number of newly occurred AK lesions between the control and the study group over one summer, counted at enrollment and follow-up. In subjects at one study site, skin DNA damage will also be assessed using cyclobutane pyrimidine dimers (CPD) levels measured by ELISA in both sun exposed (nose) and sun protected skin (buccal mucosa) in both the study and control groups. Secondary outcomes will look at clinical decreases by 25% in CPD levels after using the sensor.

## 2 INTRODUCTION: BACKGROUND INFORMATION AND SCIENTIFIC RATIONALE

### 2.1 BACKGROUND INFORMATION

The incidence of non-melanoma skin cancers (NMSC) has increased by 300% over the past 2 decades. Increasing ultraviolet (UV) exposure from the sun has been largely recognized as the primary risk factor for the development of these NMSCs. Actinic keratosis (AK) is a frequent pre-cancerous skin lesion caused by damage from ultraviolet exposure. Without treatment, 1-2% of these lesions evolve into squamous cell carcinoma (SCC)[1]. Therefore, the number of AKs reflects the effect of UV exposure and the risk for SCC. The burden of SCC is especially high in immunosuppressed patients such as transplant patients who are at high risk of skin cancer because of their immunosuppressive medications. Morbidity/mortality of SCC in transplant patients can be as high as 25%[2]. Sunscreen use has been demonstrated to decrease the number of actinic keratosis from 24%-44%[3]. However, despite, counseling and protection, UV exposure can still be difficult to control due to a variety of factors including the lack of real time UV intensity monitoring, incomplete adherence to preventive measures, and misuse of sunscreen.

### 2.2 RATIONALE

The incidence of non-melanoma skin cancers (NMSC) has increased by 300% over the past 2 decades. Increasing ultraviolet (UV) exposure from the sun has been largely recognized as the primary risk factor for the development of these NMSCs. Actinic keratosis (AK) is a frequent pre-cancerous skin lesion caused by damage from ultraviolet exposure. Without treatment, 1-2% of these lesions evolve into squamous cell carcinoma (SCC)[1].

Therefore, the number of AKs reflects the effect of UV exposure and the risk for SCC. Transplant patients are at high risk of skin cancer because of the immunosuppressive medications required to prevent organ rejection. Morbidity/mortality of SCC in this patient population can be as high as 25%[2]. Sunscreen use has been demonstrated to decrease the number of actinic keratosis from 24%-44%[3]. However, despite, counseling and protection, UV exposure can still be difficult to assess and control due to a variety of factors including UV intensity, shade, the use of protective clothing and the amount of sunscreen used. A new innovative ultraviolet (UV) sensor, Shade, helps quantify daily UV exposure and can enable users to manage their UV exposure through alerts and self-reporting through a smartphone app. In order to validate the effectiveness of Shade, we propose conducting a study looking at amount of UV exposure and the development of actinic keratosis over a 12 month period in transplant patients with a history of AKs. The study protocol will be similar to the 2015 Chen et al. NEJM paper[4] which observed a difference between 11% and 20% between their study group (nicotinamide) and the control group (placebo) in the number of actinic keratoses at 3, 6, 9, and 12 months after randomization. In addition, we will test the effect of UV exposure on cyclobutane pyrimidine dimers (CPD). These are biological markers that are increased immediately with UV exposure in a dose dependent fashion. Measurement of CPD following the delivery of a known UV dose allows for a biological readout of UV effects. In addition, CPD levels represent an equilibrium between UV induced formation and DNA repair; therefore, they can also reflect chronic UV exposure[5]. The

control group will not wear a sensor. This choice of control group allows us to provide standard of care advice to these subjects. The behavior change in the treatment group is expected to be a result of both the decision to engage with the device, for example by putting it on and opening the App as well as due to the knowledge of personal UV exposure reported by the device. We expect to gather information on the cumulative UV exposure of all subjects by using an ELISA assay for cyclopyridimine dimers (CPD) from photoexposed skin.

## 2.3 POTENTIAL RISKS AND BENEFITS

### 2.3.1 KNOWN POTENTIAL RISKS

This is a minimal risk study. All subjects will, over the duration of the study, have one dermatology visit and skin check beyond the standard of care. Subjects in the treatment group will have additional information and interaction on their UV exposure to help them make the choice to minimize such exposure.

### 2.3.2 KNOWN POTENTIAL BENEFITS

The incidence of non-melanoma skin cancers (NMSC) has increased by 300% over the past 2 decades. Vulnerable populations, such as transplant patients, have a 65 times higher risk for developing squamous cell carcinoma (SCC), and once diagnosed they have a far higher rate of developing metastases and higher mortality rate. Modification of UV exposure is difficult to teach because the rays are invisible, intuition about their intensity is demonstrably poor, and the ability to recollect exposure events is generally poor. In addition, a sudden medical change, such as immunosuppression following transplantation, can make some patients, especially skin types III-IV, become more susceptible to UV exposure and vulnerable due to limited knowledge of their daily UV requirement. The use of the UV sensor, Shade, is designed to help people manage their UV exposure by quantifying their UV exposure and alerting them of their levels through a smartphone app. The sensor is small, easy to use, and user friendly. Therefore, this device would provide an immediate benefit to study participants. In addition, if the study due to the use of Shade can demonstrate a 25% reduction in the levels of actinic keratosis (AK), and hence SCC risk, then we can extrapolate that the use of this device may decrease the morbidity and mortality of SCCs. In addition, by including a cohort of transplant patients, this study will help assess feasibility for groups at high-risk of SCC.

## 3 OBJECTIVES AND PURPOSE

This study will evaluate the safety and effectiveness of Shade for the management of UV-induced skin complications and data collected from this study will be used to support the proposed indications for use.

The purpose of this investigation is to demonstrate the safety and effectiveness of the Shade UV sensor and mobile

phone application product to reduce actinic keratosis.

## 4 STUDY DESIGN AND ENDPOINTS

### 4.1 DESCRIPTION OF THE STUDY DESIGN

This randomized partially blinded study will recruit 120 patients with a history of actinic keratosis (AK) lesions. A control versus study group analysis will be performed where 50% of the subjects will be randomly assigned (balanced by Fitzpatrick skin type, separate randomization lists will be made for type I&II and types III-VI, at time of first visit subjects will be assigned to study or control group by giving them the next assignment on the appropriate list) to use the SHADE sensor and its app (study group), while the other 50% (control group) will receive standard of care UV counseling(placebo). Subjects will have 3 visits. The first and last visit will be standard of care visits at 0 month (enrollment), and the conclusion of their involvement. The second visit will be scheduled 3 months after the enrollment visit. The final visit will be scheduled as soon as practical, but at least 3 months after visit 2 and after September 30. On arrival at each visit, study personnel will pre-screen patients to ensure that the sensor is not visible to physician prior to examination, for example by placing it in their pocket. At each follow up visit, the number of actinic keratosis on the face and hands will be counted and photographed. They will be treated as per standard of care protocol with cryotherapy or curettage. General use of field therapies will not be permitted during the trial. Any lesions suspicious of non-melanoma or melanoma skin cancer will be photographed and biopsied as part of the standard of care algorithm. Cyclobutane pyrimidine dimers (CPD) levels will be measured by ELISA from exposed (cheek) and unexposed (buccal mucosa) skin scrapings collected at the first and last visit. For each patient, the CPD level from exposed skin will be normalized to the sun protected CPD level measured from unexposed skin. We will compare the normalized CPD level of control versus study participants at each timepoint and their average CPD change over time.

We will then compare these levels with Shade UV measurements. Finally, patients will also answer questions in PROMIS (Patient-Reported Outcomes Measurement Information System) in the fields of anxiety, depression and ability to participate socially to gauge their attitudes toward the sensor

#### 4.2.1 PRIMARY ENDPOINT

1. Quantify the impact of Shade on the cumulative number of new actinic keratoses developed over the study period.

#### 4.2.3 EXPLORATORY ENDPOINTS

None

## 5 STUDY ENROLLMENT AND WITHDRAWAL

### 5.1 PARTICIPANT INCLUSION CRITERIA

1. Open to men and women of all skin types between the ages of 18-80
2. Prior history of actinic keratosis. Specifically,
  - a. Was given a diagnosis of actinic keratosis in the past year and/or has had a history of 5 or more actinic keratosis in the past 5 years.
  - b. If the patient has received a kidney transplant, the date of transplant should be longer than 6 months and should be currently on transplant immunosuppression therapy.
3. Has a smartphone that support Bluetooth low energy using a compatible operating system (iOS 8+ or Android 4+)
4. Able to commit to dermatology visits three times during the study period.

### 5.2 PARTICIPANT EXCLUSION CRITERIA

1. Has received UV therapy in the past 6 months.
2. Has had field therapy (e.g., entire face or scalp) for the treatment of actinic keratosis (e.g. topical imiquimod, 5-fluorouracil, photodynamic therapy) in the past 3 months.
3. Patient's work and or their lifestyle is not compatible with wearing a UV sensor.
4. Has difficulty controlling their own UV exposure (nursing home, long term hospitalization).
5. Has a medical condition judged incompatible with the study by the enrolling physician including the presence of an ICD or an existing plan for an extended inpatient treatment.
6. Is an employee or direct relative of an employee of the investigational site or study sponsor.
7. Must have a smartphone that is compatible with the Shade app and is comfortable using a new app (the Shade app) on their smartphone.
  - a. Jitterbug and the Samsung Galaxy J3 are not compatible with the app

Ongoing exclusion criteria:

If subject is not able to meet the commitment to ongoing visits or their answer to the exclusion criteria questions changes the subject will be removed from the study. If the change in status is temporary, less than three months, the decision to remove a subject from the study will be at the discretion of the PI.

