### 5.4.1 REASONS FOR WITHDRAWAL OR TERMINATION

Participants who can not comply with the requirement for quarterly visits will be dropped from the study.

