### 5.4.2 HANDLING OF PARTICIPANT WITHDRAWALS OR TERMINATION

Subject compensation will not be affected by study withdrawal or termination. Each endpoint will be analyzed using only data for which there is a complete data set relevant to that analysis.

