### 7.3.5 EARLY TERMINATION VISIT

Subjects who withdraw consent or otherwise voluntarily leave the study will be offered the opportunity to participate in the next visit scheduled for the study.

Subjects who are dropped from the study for any reason will be contacted by phone to explain the reason they have been dropped from the study. An early termination visit is not required.

Subjects who terminate early will be asked to return their Shade device and will be given the same offer to obtain a new device of their own as subjects who complete the study.

The study coordinator will fill out a study termination form for all subjects including those who leave early.

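### Section 5.2 re-applies the exclusion questions after randomisation and removes subjects whose answer changes, so they can drop out of the primary comparison for reasons that may be related to AK burden or arm

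*Combined protocol and SAP*

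**What the plan says.** Section 5.2 of the combined protocol and SAP ends with a paragraph of ongoing exclusion criteria. If a subject cannot keep to the visits, or "their answer to the exclusion criteria questions changes the subject will be removed from the study". There is one exception. Where the change is temporary, lasting less than three months, "the decision to remove a subject from the study will be at the discretion of the PI".

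Three of the re-applied criteria matter most here:

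- Criterion 2: "Has had field therapy (e.g., entire face or scalp) for the treatment of actinic keratosis" within the past 3 months.
- Criterion 3: the patient's work or "lifestyle is not compatible with wearing a UV sensor".
- Criterion 7: the patient has a compatible phone and "is comfortable using a new app (the Shade app) on their smartphone".

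Section 5.4.1 adds a second removal rule: "Participants who can not comply with the requirement for quarterly visits will be dropped from the study".

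Two other sections settle what happens to removed subjects. Section 7.3.5 says that those who are dropped are told by telephone, and "An early termination visit is not required". Subjects who leave by their own choice are at least offered the next scheduled visit. Section 5.4.2 says: "Each endpoint will be analyzed using only data for which there is a complete data set relevant to that analysis". Section 10.3 describes how datasets are prepared but defines no analysis population, so nothing there brings removed patients back.

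**The concern.** An entry criterion applied before randomisation affects both arms alike. The same criterion applied afterwards can act differently in the two arms, because the answer may by then depend on the outcome or on the allocation.

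- **Burden.** A patient who develops many AKs is the likeliest to receive field therapy. If the device works, such patients should be more common among controls. Losing them would shrink the observed effect.
- **Arm.** Section 2.2 states that controls wear no sensor. Incompatibility with the sensor, or discomfort with the app, can therefore be discovered in use only in the device arm. If the patients removed for this reason tended to have high counts, the device would look better than it is.

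Removed patients have no further required AK count, so the primary analysis would compare what remains of each arm and not the groups as randomised.

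**Working it through.** **1. Does anything keep a removed patient in the analysis?** Section 5.2 mandates removal, 7.3.5 requires no outcome visit, 5.4.2 uses complete data, and 10.3 defines no intention-to-treat set. A patient removed before the final visit has no complete cumulative AK count. The discretion clause does not reach criteria 1 and 2. They look back 6 and 3 months, so a changed answer does not clearly count as lasting less than three months.

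**2. Calibrating the dispersion.** Section 10.5 gives a power of 0.81 for a 25% reduction with 50 per arm and a one-tailed t-test. It does not tabulate the AK distribution, so the figure can be back-solved but not verified. With the normal approximation:

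- d = (1.645 + 0.878) × √(2/50) = 0.5045
- SD/mean = 0.25 / 0.5045 = 0.4955

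With that ratio, 60 per arm (the 120 patients of section 4.1) and the two-tailed 0.05 test of section 10.4.1, power with nobody removed is 0.789.

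**3. Simulation model (assumed).** Patient rates are gamma-distributed and counts are Poisson. The mean AK counts are 5, 10 and 20, with rate CVs of 0.33, 0.45 and 0.51. Check for mean 10, as variances relative to the control mean squared:

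- control: 0.45² + 1/10 = 0.3025
- device: 0.75² × 0.45² + 0.75/10 = 0.1889
- root of the average: √0.2457 = 0.496, which matches step 2.

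**4. Removing 3 of 60 (5%) from one arm only**, two-tailed Student's t-test:

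| Scenario | True 25% effect, controls removed | No effect, device patients removed |
|---|---|---|
| Nobody removed | 25%; power 0.76-0.79 | 0%; false-favourable rate 0.025 |
| Weighted by the patient's rate squared | 23-24%; power 0.69-0.73 | 1-2% spurious; 0.03-0.05 |
| The three highest counts | about 19%; power 0.55-0.59 | about 7% spurious; about 0.11-0.13 |

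**5. Hand check of the weighted row.** With weights proportional to rate squared, a removed patient's expected rate is m(1 + 2CV²). The 57 who remain then average m(1 − 6CV²/57).

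- CV 0.33: a fall of 6 × 0.1089/57 = 1.1%. A true 25% becomes 1 − 0.75/0.9885 = 24.1%.
- CV 0.51: a fall of 6 × 0.2601/57 = 2.7%. A true 25% becomes 1 − 0.75/0.9726 = 22.9%.

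The formula slightly overstates the fall, because the draw is without replacement from only 60 patients. It agrees with the simulation.

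**6. What drives the bias.** These are separate runs with no device effect, mean 6 and 4,000 repetitions:

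- Random removal of 10%, in one arm or both: no material bias, type I error 0.044-0.051.
- Burden-weighted removal of 10% in both arms: no spurious reduction.
- Burden-weighted removal of 10% of the device arm only: about 1% spurious (type I error 0.052) at a count CV of 0.495, but about 13% (0.132) at a CV of 1.0.
- Burden-weighted removal of 20% against 0%: about 3% (0.065) and 26% (0.362) at the same two CVs.

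A CV of 1.0 does not fit the plan's own power. With 50 per arm it would give 0.346 one-tailed.

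**The case against.** The field-therapy route is already narrow. Section 4.1 does not permit general use of field therapies. Section 7.6 prohibits them, and also prohibits AK treatment by an outside dermatologist. AKs found at visits are treated individually. Criterion 2 would therefore change mainly through a protocol deviation. This stands, and it lowers the likely frequency. It does not say what happens to the data of a patient who deviates.

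The arm-linked route is also an inference. Criterion 3 says nothing about outdoor habits or AK counts. Section 7.3.3 offers device-arm patients counselling, training and replacements. Some who give up the sensor early would be excluded anyway by the under-15%-use filter in 10.4.2. That too stands, although the filter acts on the analysis, whereas section 5.2 ends data collection.

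A reader might infer several stronger things that the documents do not support:

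- **That the comparison will be seriously biased in a known direction.** No removal rate is given, the two routes pull in opposite directions, and the large figures need either the extreme selection or dispersion well above what the stated power implies.
- **That criteria 4 and 5 (loss of control over UV exposure, medical condition) bias the comparison.** They have no stated arm link. Equal loss in both arms mainly affects generalisability.
- **That investigator discretion unblinds the AK counts.** A sensor-related reason would reveal the arm to the PI, but the documents do not say that the PI does the counting.
- **That section 5.4.1 sets a real quarterly schedule.** Section 17.2 shows that visits were removed, so the word appears to be left over.
- **That nothing can be done with the data.** Baseline counts, and second-visit counts for later removals, would support sensitivity analyses, though not replace the missing outcome.

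**Conclusion.** The point holds as a weakness in retention and in the analysis population. As written, a changed exclusion answer takes a randomised patient out of follow-up and out of the primary comparison, and the reasons may be related to AK burden or to arm. Bias arises only if removal is both related to burden and unequal between arms.

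At the dispersion implied by the stated power, a plausible 5% one-sided loss moves the estimate by 1 to 2 percentage points and costs roughly 0.03 to 0.10 of power. Losing exactly the three highest counts is the extreme case, and more skewed counts would make the bias larger. All of this rests on assumed removal rates, selection weights and a gamma-Poisson model, because the protocol gives neither the AK distribution nor an expected removal rate. It should be fixed, because a count that was never taken cannot be recovered later.

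**What to change.** - **Section 5.2:** apply the exclusion criteria once, before randomisation. Replace the ongoing-criteria paragraph with wording to this effect: *a change in an exclusion answer after randomisation is recorded with its date; stopping use of the device is distinct from leaving the study; AK counts at visits 2 and 3 continue to be collected unless the subject withdraws consent.*
- **Sections 5.4.2, 7.3.5 and 10.3:** state that all randomised patients with AK counts are analysed in their assigned group. Add a sensitivity analysis for missing counts, and another for patients who received prohibited field therapy.
- **Section 5.4.1:** reconcile the reference to quarterly visits with the three-visit schedule in sections 4.1 and 5.1.

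No change to permitted treatments or their timing is proposed. The cost is protocol wording and a few patients seen at visits already planned. The small downside is that some retained counts will be affected by off-protocol therapy, which is what the second sensitivity analysis is for.
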